7.1 Screening visit

7.1.1 Subject Enrollment

If the subject has met the preliminary study criteria the PI, and/or his designee, will;

- Obtain an informed consent from the subject, clearly stating that the subject is willing to undergo the screening procedure and indicating subject understanding of the requirements and risks involved with study participation and other applicable treatment options. The informed consent will also include photo release consent, stating that the subject is allowing the sponsor (Alma Ltd.) to use the photos taken during the study for educational and marketing purposes (subject identity will be masked to the best possible extent in these pictures).
- Collect demographic characteristics and general information (DoB, Ethnicity, BMI, previous smoking habits and physical activity).
- Review the subject's medical history and concomitant medications use.
- Screen the subject for eligibility to participate in the clinical study using the Inclusion and Exclusion criteria.
- Confirm negative results of pregnancy urine test.
- Perform physical examination and vital signs assessment.
- Document the designated treatment area (lower abdomen w/wo flanks or outer thighs w/wo inner thighs)
- Document if the subject is eligible for facial fat grafting.

If the subject has met the eligibility criteria, he/ she will be recruited to the study.

7.1.2 Subject Identification

At enrollment, each subject will receive a unique identifying number that will be composed of a consecutive number and subject initials. This unique identifier will be used throughout the entire study and will be entered in the subject's CRF for each visit.

7.1.3 Scheduling surgery visit and referral to pre-surgery examinations

Subjects recruited to the study will be scheduled for a surgery up to 2 months after enrollment and for pre-surgery evaluation visit one week prior to the surgery.

- Subjects will be instructed to perform the following optional examinations, per local institution regulation, prior to the pre-surgery evaluation visit;
 - Blood tests including; CBC (complete blood count), chemistry screening and blood clotting test (coagulation tests).
 - Staph MRSA screen test nasal swab test. If positive, the subject will receive treatment for 5 days prior to the surgery.
 - E.K.G (for subjects > 40 years old).
 - Chest X-ray (for subjects > 50 years old or with relevant background diseases).

All examinations should be performed up to 2 months prior to the surgery.

 At Sanctuary Plastic Surgery, US site subjects will be referred to perform Magnetic Resonance Imaging (MRI) for abdominal fat thickness assessment and facial fat volume assessment.

7.2 Pre-Surgery evaluation visit

At the pre-surgery evaluation visit the study investigator, and/or his designee will perform pre-surgery evaluations, provide instructions to the subjects and perform baseline assessments.

7.2.1 Pre-surgery evaluations

The study investigator, and/or his designee will;

- Review examinations results (detailed in section 7.1.3) and evaluate subject's suitability to the surgery.
- Perform physical examination.
- Evaluate any change in Inclusion/ Exclusion Criteria.

In addition, the subject will meet with an anaesthesiologist, who will give his approval to the surgery (optional, per local institutional regulation).

7.2.1 Pre surgery instructions

Subjects will be recommended to bring to the surgery; abdominal garment (for abdominal liposuction) and wear it for at least 2 weeks after the surgery or thigh garment (for thigh liposuction) and wear it for at least 1 month after the surgery.

7.2.2 Baseline assessments

The study investigator, and/or his designee will;

- Monitor subject adverse events.
- Assess the changes in medication intake since last visit.
- Measure subject's body weight.
- Photograph the subject, only treated area, without the face, while the subject
 is standing with hanging arms. At Assaf Harofeh site, when using a 2D camera,
 photograph the subject at frontal, back, 45 and 90 degrees positions, according
 to a standardized photography instructions (refer to section 8.4).
- For subjects that intended to undergo facial fat grafting procedure, photograph the subject's face at frontal, 45 and 90 degrees positions, when using 2D camera (refer to section 8.4).
- At Sanctuary Plastic Surgery site confirm and document results from the MRI,
 i.e. abdominal fat thickness and facial fat volume.

The pictures taken in this study may be used by the Sponsor (Alma Lasers Ltd.) in the future for educational and marketing purposes. Subjects' identity will be masked to the best possible extent in these pictures.

7.3 Surgery visit

7.3.1 Reevaluation

Prior to the surgery, the study investigator, and/or his designee will;

- Evaluate any change in Inclusion/ Exclusion Criteria.
- Confirm negative results of pregnancy urine test.
- Assess the changes in medication intake since last visit.
- Monitor subject adverse events.
- Perform physical examination and vital signs.

7.3.2 Surgery Procedure

Perioperative antibiotic will be administered, per surgeon's discretion.

During the surgery, the study investigator, and/or his designee will perform laser assisted liposuction using the LipoLifeTM system, including:

- 1. Instilment of tumescent containing local anesthesia to the treated area (abdomen w/wo flanks or outer thighs (w/wo inner thighs), using the LipoFlow peristaltic mode.
- 2. Harvest of adipose tissue (1-3 liters) from the treated are, using the Lipoflow suction mode and LipoDiode CW mode.

The LipoLifeTM system is designed to be operated only by licensed medical practitioners properly trained in its handling and use. Personnel operating the device must read the operator's manual.

For facial fat grafting procedure (if relevant) the procedure will also include;

3. Injection of the harvested adipose tissue into the face, at least 5 cc per cheek, using the standard fat grafting equipment i.e. syringe, blunt cannula etc.

For fat vitality assessment (optional), ten (10) samples of the harvested fat, from 10 subjects at Assaf Harofeh MC, will be transported to the laboratory, within 4 hours. Cell viability assessment will be performed using trypan blue exclusion assay.

7.3.3 Post-surgery instruction

The subject will usually be discharged from the hospital at the same day or a day after the surgery, according to local institutional regulation, with recommendations to rest for two weeks, wash the surgical area with water and soap, and wear the abdominal/thigh garment on a daily basis. In addition, a 1 month follow-up meeting will be scheduled.

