3.2.3 Procedure and parameters

Prior to performing the liposuction procedure, local anaesthesia is administered using the LipoFlow peristaltic mode. Tumescent fluid usage is 150 cc to 500 cc for a $10 \times 10 \text{ cm}^2$ area, while the anticipated total mg/kg dosage of tumescent lidocaine should not exceed 45 mg/kg.

Approximately 20–30 minutes should be allowed to enable an adequate diffusion of the tumescent solution and provide effective vasoconstriction.

Liposuction with the LipoLifeTM system involves simultaneous work of laser and suction. Alma 1470 diode laser is used in Continuous Wave (CW) emission mode, Pulse mode and Repeat mode. Power settings are recommended to be selected as a function of the liposuction area: 10-13W (chin, arms and knees), 13W (abdomen, back), and 15W (thighs, hips and buttocks). The laser energy is conveyed into the fat layer using a 3mm cannula which incorporates a 400 or $600\mu m$ optical single-use fiber. The suction tube is connected directly to the cannula so laser and suction will work simultaneously.

The LipoLifeTM system is designed to be operated only by licensed medical practitioners properly trained in its handling and use. Personnel operating the device must read the operator's manual.

4 Study Objectives

4.1 Primary objective:

To evaluate the efficacy of Laser Assisted Liposuction procedure with the LipoLife TM system.

4.2 Secondary objectives:

- To evaluate the efficacy of facial fat grafting procedure using autologous fat harvested with the LipoLifeTM system.
- To evaluate subjects' satisfaction.
- To evaluate procedure related safety.
- To evaluate fat vitality of the harvested fat with the LipoLifeTM system (optional).

5 Study Design

This is a multi-center, prospective, open label, single arm study.

The study will include 6 visits at the medical center: screening, pre-surgery evaluation visit, laser assisted liposuction surgery w/wo facial fat grafting and 3 follow up visits.

Following the screening visit, eligible subjects will be enrolled into the study. Each subject will undergo laser assisted liposuction surgery w/wo facial fat grafting (5-20 subjects), using the LipoLifeTM system. Pre-surgery evaluation visit will be carried out 1 week prior to the surgery. Follow up visits to evaluate safety and efficacy will take place at 1, 3 and 6 months after the surgery (See Figure 5 for an illustration of the study design).

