7.4 Follow-Up visits

Follow up visits will be carried out 1 month ±7 days (1m FU), 3 months ±7 days (3m FU) and 6 months ±7 days (6m FU) after the surgery.

During these visits the following procedures will be performed by the investigator, and/or his designee:

- Assessment of changes in medication intake since last visit.
- Physical examination and vital signs.

 Assessment of adverse events according to subject's report and physical examination.

- Obtaining subjects' satisfaction, following liposuction procedure, according to subject's satisfaction questionnaire (see section 8.3).
- Body weight measurement.
- Subjects' liposuction area photography, according to standardized photography instructions (see section 8.4).
- For subjects that had fat grafting procedure:
 - Facial photography, according to standardized photography instructions (see section 8.4).
 - Obtaining subjects' satisfaction, following facial fat grafting procedure, according to subject's satisfaction questionnaire (see section 8.3).
- At Sanctuary Plastic Surgery site, at 1m FU visit subject will be referred to perform MRI for abdominal fat thickness assessment and facial fat volume assessment, 2-3 weeks prior to the 3m FU visit. At 3m FU visit, the investigator, and/or his designee will confirm and document the results from the MRI assessments.

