9.5 Recording of AEs and SAEs

When an AE/SAE occurs, it is the responsibility of the investigator to review all documentation (e.g. hospital progress notes, laboratory, and diagnostic reports) relative to the event. The investigator will then record all relevant information regarding an AE/SAE in to the CRF. It is not acceptable for the investigator to send photocopies of the subject's medical records to Alma Lasers Ltd. in lieu of completion of the appropriate AE/SAE CRF pages. However, there may be instances when copies of medical records for certain cases are requested by Alma Lasers Ltd. In this instance, all subject identifiers will be blinded on the copies of the medical records prior to submission to Alma Lasers Ltd.

For each adverse event, start and stop dates, action taken, outcome, intensity and relationship to study product (causality) must be documented. If an AE changes in frequency or intensity during a study, a new entry of the event must be made in the CRF.

The investigator will attempt to establish a diagnosis of the event based on signs, symptoms, and/or other clinical information. In the absence of a diagnosis, the individual signs/symptoms should be documented. All details of any treatments initiated due to the adverse event should be recorded in the subject's notes and the CRF.

9.6 Prompt Reporting of SAEs to Alma Lasers Ltd.

Once an investigator becomes aware that an SAE has occurred in a study subject, he/she will immediately notify the sponsor by contacting the study monitor via telephone to notify him/her of the event. The SAE form must be completed as thoroughly as possible with all available details of the event, signed by the investigator, and faxed within 24 hours of first becoming aware of the event to the following person:

[name]

Alma Lasers Ltd. [name]

[contact] [contact]

If the investigator does not have all information regarding an SAE, he/she will not wait to receive additional information before notifying the study monitor of the event and completing the form. The form will be updated when additional information is received.

The investigator must also notify the Reviewing IRB/ Helsinki/ other ethic Committee of any SAEs according to the guidelines of the Ethics Committee.

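### No adverse event assessment is scheduled between surgery and the 1-month visit, so early non-serious events that resolve unreported rest largely on recall

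*Combined protocol and SAP*

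**What the plan says.** Section 5 sets six visits, three of them after surgery. On discharge, 7.3.3 states: "The subject will usually be discharged from the hospital at the same day or a day after the surgery". It adds advice on two weeks' rest, washing and the garment. The next contact it names is the 1-month one: "In addition, a 1 month follow-up meeting will be scheduled".

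Section 7.4 times that visit as follows: "Follow up visits will be carried out 1 month ±7 days (1m FU". Table 1 gives the same visit as 4 weeks ±7 days. At follow-up visits the AE method is "Assessment of adverse events according to subject's report and physical examination".

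For the surgery visit, AE monitoring appears in 7.3.1, in a list that opens "Prior to the surgery, the study investigator, and/or his designee will". Sections 7.3.2 and 7.3.3 specify no AE check after the operation.

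For each event, 9.5 requires "start and stop dates, action taken, outcome, intensity" and causality, with a new entry whenever frequency or intensity changes. Section 9.7.1 grades intensity by how far the event interferes with everyday activities.

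Other provisions keep reporting open. The opening of section 9 has AEs recorded from consent to final follow-up. Section 9.2 has anticipated AEs reported whenever they occur. Section 9.6 requires immediate notice of a serious AE once the investigator knows of it. Section 9.5 has the investigator review the medical documentation.

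**The concern.** Procedure-related safety is a secondary objective (4.2), and AEs and serious AEs are its endpoints (5.1.2). Several of the events that 9.2 anticipates, such as local pain, haematoma, infection and ecchymosis, can plausibly arise early and clear within weeks. An examination at one month cannot find an event that has already gone. If the subject did not report it at the time, it reaches the case report form only if it is remembered at the interview, and its dates and intensity are then reconstructed three to five weeks later.

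With no control arm, under-ascertainment cannot cancel between groups. It lowers the reported rate, which favours the device. It also weakens the severity grading and the dates that 9.5 asks for.

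**Working it through.** **Step 1. Scheduled AE checks, in order.**
- Pre-surgery evaluation, one week before surgery (7.2.2).
- Surgery visit, before the operation (7.3.1).
- Follow-up visits at 1, 3 and 6 months (7.4).

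The five marks in the AE row of Table 1 match these five checks and add none. No visit, call or diary is described between the operation and the 1-month visit. As written, the gap therefore starts at surgery rather than at discharge.

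**Step 2. Length of the gap.** The plan states no recall interval, so there is no figure to reproduce. With target day T, the visit falls between T − 7 and T + 7 days after surgery. Counting from a day-1 discharge takes one day off each end.

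| Source | T | From surgery | From day-1 discharge |
|---|---|---|---|
| Table 1, 4 weeks | 28 | 21 to 35 | 20 to 34 |
| 7.4, 30-day month | 30 | 23 to 37 | 22 to 36 |
| 7.4, 31-day month | 31 | 24 to 38 | 23 to 37 |

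The two statements of the window differ by 2 to 3 days. Even the earliest visit, on day 21, falls a week after the two weeks of recommended rest end (21 − 14 = 7).

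**Step 3. Which early events have a route other than recall.**

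| Early event | Route |
|---|---|
| Serious, known to the investigator | Immediate notice, form within 24 hours (9.6) |
| Reported by the subject | Recorded in the case report form (section 9, 9.2) |
| Documented in hospital, laboratory or diagnostic records | Record review (9.5) |
| Treated with medication | Medication changes asked about at each follow-up visit (7.4) |
| Still present at the visit | Physical examination (7.4, 8.2) |
| Non-serious, resolved, untreated, unreported and undocumented | Recall at the visit only |

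Only the last row is exposed. The open routes need the event to reach the investigator first, and section 9 ties active detection to safety evaluations, none of which is scheduled in this interval.

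**Step 4. Effect on the reported incidence.** With 20 subjects (6.1), one subject whose only event is missed lowers the proportion with any AE by 1/20 = 5 percentage points. Section 6.3 asks for 10% over-enrolment. If all 20 × 1.10 = 22 were treated and counted, the step is 1/22 = 4.5 points. If the subject has another recorded event, the incidence does not move and only the event count falls, by one.

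**Step 5. How many events are missed.** The documents give no resolution times, no expected early event rate for these procedures and no recall loss, so no total can be calculated.

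**The case against.** A reader might infer from the schedule that no AE data at all are collected in the first month. The documents do not support that. Section 9, 9.2, 9.5 and 9.6 keep collection open from consent onwards, and 11.12 adds the reporting of serious adverse device effects. What is missing is a scheduled assessment, not collection itself.

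Nor do all early events rest on recall. Records, medication review and examination cover many of them. Some anticipated events in 9.2, such as contour deformity, scar fibrosis and fat necrosis, may well persist to the visit.

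A reader might also take the AE rate to be the only safety summary. Section 10.3 also specifies a detailed AE list, compilation by nature, seriousness, severity and relationship, and listings of all safety measures. These provisions do limit the damage. However, a list of events carries the same omissions as the rate if the events never reach the form.

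The analysis is descriptive (10.1), with no safety threshold or comparator, and the three intensity grades are coarse. This is a fair reason to rank the point low. The consent form is not among the documents reviewed and may ask subjects to report symptoms as they occur. That would help, although it would not supply dated records.

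What stands is narrow: for events that are non-serious, resolved, unreported and undocumented, the plan offers one late interview.

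**Conclusion.** The point holds in this limited form and is a cheap improvement, not a flaw that undermines the study. No AE assessment is scheduled between the operation and a visit on day 21 to 35 (Table 1) or about day 23 to 37 (7.4, taking a month as 30 days). A defined subset of early events therefore rests largely on recall, although the plan requires dates and intensity for them.

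The direction of any under-count is clear: it favours the device. The number of missed events is unknown. Any percentage of events lost to recall would be an assumption from outside the documents, and the conclusion does not need one. The step of 5 percentage points per subject assumes a denominator of 20 and that the missed event is the subject's only one.

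**What to change.** Make three small changes.

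1. **Section 7.3.3:** give each subject a one-page dated AE diary at discharge, with columns for symptom, start date, stop date and effect on daily activity. The last column supplies what the intensity grades in 9.7.1 depend on.
2. **Section 7.4 and Table 1:** collect the diary at the 1-month visit and use it as a source for the AE form, alongside the interview and examination. The investigator still decides what is an AE and grades it.
3. **Section 7.4 and Table 1:** reconcile the two statements of the 1-month window, so that an in-window visit has one definition.

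None of this adds a visit or a procedure, or changes care. The cost is one printed page, slight subject burden and, on a plain reading of 11.8, a protocol amendment with ethics approval at both sites. The reported AE count will probably be somewhat higher, and the report should say that a diary was used so that readers can interpret the rate.

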7.4 Follow-Up visits

Follow up visits will be carried out 1 month ±7 days (1m FU), 3 months ±7 days (3m FU) and 6 months ±7 days (6m FU) after the surgery.

During these visits the following procedures will be performed by the investigator, and/or his designee:

- Assessment of changes in medication intake since last visit.
- Physical examination and vital signs.

 Assessment of adverse events according to subject's report and physical examination.

- Obtaining subjects' satisfaction, following liposuction procedure, according to subject's satisfaction questionnaire (see section 8.3).
- Body weight measurement.
- Subjects' liposuction area photography, according to standardized photography instructions (see section 8.4).
- For subjects that had fat grafting procedure:
 - Facial photography, according to standardized photography instructions (see section 8.4).
 - Obtaining subjects' satisfaction, following facial fat grafting procedure, according to subject's satisfaction questionnaire (see section 8.3).
- At Sanctuary Plastic Surgery site, at 1m FU visit subject will be referred to perform MRI for abdominal fat thickness assessment and facial fat volume assessment, 2-3 weeks prior to the 3m FU visit. At 3m FU visit, the investigator, and/or his designee will confirm and document the results from the MRI assessments.

7.5 Termination visit

The termination visit occurs in parallel with the last follow up visit (6m FU visit). During this visit the coordinator/investigator will fill the termination CRF.

7.6 Summary of study procedures

Schedule of times and events, including required study visits, procedures and assessments to be performed at each visit can be found at the table below (Table 1).

Table 1: Study Procedures- ALM-Lipo-001

FU=follow up; m= month; W=week; d=days

	Visit 1	Visit 2	Visit 3	Visit 4	Visit 5	Visit 6
	Screening	Pre- Surgery evaluation	Surgery	1m FU	3m FU Primary endpoint	6m FU
Weeks	Up to -2m	-1w	0	4W ±7d	12W ±7d	24W ±7d
Informed consent	Х					
Demographic assessment	Х					
General information (previous smoking habits and physical activity)	х					
Medical History	Х					
Concomitant Medications	Х					
Concomitant Medications change		Х	Х	Х	Х	Х
Physical examination	Х	Х	Х	Х	Х	Х
Vital signs	Х		Х	Х	Х	Х
Pregnancy test	Х		Х			
Inclusion/Exclusion Criteria assessment	х					
Inclusion/ Exclusion Criteria evaluation for change		х	Х			
Pre/ Post-surgery instructions to the subjects		х	Х			
Review pre-surgery examinations (optional) e.g.; Blood test, Staph NRSA screen test, E.K.G and chest X-Ray		х				
Consultation with an anesthesiologist (optional)		Х				

Visit 1 Visit 2 Visit 3 Visit 4 Visit 5 Visit 6 3m FU Pre-6m FU Screening Surgery Surgery 1m FU Primary evaluation endpoint Weeks Up to -2m -1w 0 4W ±7d 12W ±7d 24W ±7d Liposuction procedure-Subject's satisfaction questionnaire Χ Χ Χ (5 point Likert scale) Facial fat grafting procedure -Subject's satisfaction questionnaire Χ Χ Χ (5 point Likert scale)* Χ Body weight measurement Χ Χ Χ Liposuction area (when using 2D camera at Assaf Χ Χ Χ Harofeh MC: Χ Frontal, back, 45 and 90 degrees Subject positions) photography** Face* (when using 2D camera at Assaf Χ Χ Χ Х Harofeh MC: Frontal, 45 and 90 degrees positions) Blinded evaluations Χ Χ Χ MRI results *** (abdominal fat thickness and facial Χ Х fat volume) AE assessment Χ Χ Χ Χ Χ **Termination CRF** Χ

^{*} For subject that will have/had facial fat grafting procedure.

^{** 3}D camera at Sanctuary Plastic Surgery, US and 2D or 3D camera at Assaf Harofeh MC, Israel

^{***} At Sanctuary Plastic Surgery, US

8 Evaluations

